7.7 Laboratory Parameters

Data collected from the central and local laboratories, including additional laboratory testing due to an SAE, will be used in all analyses. All values will be assessed based on National Cancer Institute Common Terminology Criteria for Adverse Events (NCI CTCAE 4.0). The highest grade will be used if lab results are collected on the same date.

All laboratory parameters will be summarized for analysis sets 2 – 3 specified in [Table 3](#). The laboratory parameters summaries for Study M14-212 are available in the CSR.

7.7.1 Assessment of Shifts from Baseline in Clinical Laboratory Parameters

For shifts relative to NCI CTCAE grading, baseline and post-baseline laboratory observations will be categorized as Grade 0, Grade 1, Grade 2, Grade 3, or Grade 4 according to NCI CTCAE grade version 4.0. For each parameter, shift tables will be generated that cross tabulate the number of subjects with baseline values of Grade 0, Grade 1, Grade 2, Grade 3, or Grade 4 versus final observations of Grade 0, Grade 1, Grade 2, Grade 3, or Grade 4. Additionally, for each parameter, the number and percentage of subjects that have a baseline observation that is categorized as a Grade 0 to Grade 2 and have a Grade 3 or 4 final observations will be presented. In addition to the final observation, a similar summary will be produced for the maximum post-baseline NCI CTCAE grade.

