An Interactive Response Technology (IRT) system will be utilized to register subjects. Once the subject has signed the informed consent the site will obtain a screening (subject) number via the IRT system. Once the screening number is assigned, if the subject is not enrolled into the study, the reason for screen failure will be documented in the source document and will be captured in the eCRF.

The results of all screening evaluations must be within clinically acceptable limits, upon review by the investigator before a subject can be administered study drug. Subjects will not be enrolled in the study if laboratory or other screening results are unacceptable.

Subjects who complete all screening procedures and meet the eligibility criteria in Section 5.2.1 and none of the exclusion criteria in Section 5.2.2 will proceed to enrollment.

Post-Treatment Follow-Up Visit(s)

For subjects who discontinue study treatment for reasons other than disease progression, the following post-treatment assessments will be performed every 12 weeks (\pm 1 week) until criteria are met for discontinuation from the study (e.g., disease progression, death or a subject's refusal of the Post-Treatment visits) for a period of 1 year after last subject's last dose or possibly sooner if all patients have discontinued and most patients have expired:

- Hematology
- Disease Assessment

Survival Assessment(s)

Survival information (e.g., date and cause of death, post-treatment cancer therapies, including transplantation) will be collected once the subject's disease has progressed via telephone calls (e.g., to subject or family member) and/or clinical visits at 12 weeks intervals (\pm 1 week) after the subject's last study visit for a period of 1 year after last subject's last dose or possibly sooner if all patients have discontinued and most patients have expired.

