8.1.4.4 Longitudinal Analyses of Laboratory and Vital Signs Data

Changes from baseline will be analyzed for each scheduled post-baseline visit and for the final visit for blood chemistry and hematology parameters, as well as urinalysis and vital sign parameters. If more than one measurement exists for a subject on a particular day, then an arithmetic average will be calculated. This average will be considered to be that subject's measurement for that day. Post-baseline measurements more than 30 days after the last dose of study drug will not be included. Subjects that do not have a baseline measurement or do not have any post-baseline measurements will not be included.

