8.1.4.5 Analyses of Laboratory Data Using NCI CTCAE

Where applicable, blood chemistry, hematology and lymphocyte enumeration determinations will be categorized according to NCI CTCAE Version 4.0⁴⁰ grades, and

shifts from baseline NCI CTCAE⁴⁰ grades to maximum and final post-baseline grades will be assessed.

The baseline and final grades will be defined respectively as the grade of the last measurement collected prior to the first dose of study drug, and as the last post-baseline measurement collected no more than 30 days after the last dose of study drug. The percentage of subjects experiencing a shift from baseline grades of 0 to 2 to maximum post-baseline grades of 3 to 4, and from baseline grades of 0 to 2 to final post-baseline grades of 3 to 4 will be summarized.

Detailed listings of data for subjects experiencing NCI CTCAE⁴⁰ grade 3 to 4 blood chemistry and hematology values will be provided. All measurements collected, regardless of the number of days after the last dose of study drug, will be included in these listings.

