7.1 Analysis Conventions

All data available in the extracted database will be used in the safety analyses.

Definition of Study Drug

Unless otherwise specified, the study drug in this document refers to

- Venetoclax (Study M14-212)
- Venetoclax and HMA (Study M14-358)

- Venetoclax and LDAC (Study M14-387)

Definition of Baseline

All baseline summary statistics and analyses will be based on characteristics prior to the initiation of any component of study drug. Unless otherwise stated, baseline for a given variable will be defined as the last value for that variable obtained prior to the first dose of any component of study drug.

Definition of Study Day

Study Day is defined as the number of days since (positive numbers) or prior to (negative numbers) the first dose of study drug. The day of the first dose of study drug is defined as Study Day 1, while the day prior to the first dose of study drug is defined as Study Day -1; there is no Study Day 0.

Definition of Final Observation

The final observation is defined as the last non-missing observation collected after the first dose of study drug to the last dose of study drug + 30 days.

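### The maximum post-baseline CTCAE grade has no end date in the safety SAP, so an off-treatment hematology value can be tabulated as the worst grade

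*SAP*

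**What the plan says.** Safety SAP 7.7.1 plans shift tables from the baseline grade to the final observation, and then a second set: "In addition to the final observation, a similar summary will be produced for the maximum post-baseline NCI CTCAE grade". Section 7.7.3 repeats the Grade 0-2 to Grade 3-4 shift by sex, age, race and region, using the maximum grade only.

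Safety SAP 7.1 defines the final observation as the "last non-missing observation collected after the first dose of study drug to the last dose of study drug + 30 days". It has no matching definition for the maximum. On scope, 7.1 states: "All data available in the extracted database will be used in the safety analyses". Section 7.7 adds: "Data collected from the central and local laboratories, including additional laboratory testing due to an SAE, will be used in all analyses".

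Protocol 8.1.4.5 plans shifts to both maximum and final grades. It defines the final grade from the last post-baseline "measurement collected no more than 30 days after the last dose of study drug" and gives the maximum no window. For the Grade 3-4 listings it says: "All measurements collected, regardless of the number of days after the last dose of study drug, will be included in these listings". Protocol 8.1.4.4, on changes from baseline, says: "Post-baseline measurements more than 30 days after the last dose of study drug will not be included".

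On data collection, protocol 5.3.1.1 says: "For subjects who discontinue study treatment for reasons other than disease progression, the following post-treatment assessments will be performed every 12 weeks". The assessments are hematology and disease assessment. They run up to 1 year after the last subject's last dose, or possibly less.

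**The concern.** The two shift tables in 7.7.1 look parallel, but only one has an end date. The protocol schedules blood counts well after study drug stops, so late values exist by design. A programmer who follows the text literally would let such a value set the subject's maximum grade. A low platelet or neutrophil count found months after the last dose, for instance at the visit that detects relapse, would then appear as the worst grade under venetoclax plus low-dose cytarabine. An adverse event with the same onset date would be excluded by 7.6. The subgroup tables in 7.7.3 would be exposed throughout, because they use no other grade.

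**Working it through.** The documents give no figure to reproduce. The check compares the windows, then the visit timing, then the conditions under which a late value matters.

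**1. Windows side by side**

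| Output | Place | End of window |
|---|---|---|
| Final observation | Safety SAP 7.1 | Last dose + 30 days |
| Treatment-emergent adverse events | Safety SAP 7.6 | Last dose + 30 days |
| Days in hospital | Safety SAP 7.6.3 | Last dose + 30 days |
| Maximum grade, all subjects | Safety SAP 7.7.1 | None stated |
| Maximum grade, subgroups | Safety SAP 7.7.3 | None stated |
| Final grade | Protocol 8.1.4.5 | Last dose + 30 days |
| Maximum grade | Protocol 8.1.4.5 | None stated |
| Change from baseline | Protocol 8.1.4.4 | Last dose + 30 days |
| Grade 3-4 listings | Protocol 8.1.4.5 | None, stated explicitly |

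No other section of either document bounds the maximum grade. The only implicit end is the data extraction date.

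**2. Do values exist outside 30 days?** Post-treatment visits are every 12 weeks ± 1 week. If they are counted from the end of treatment, the first falls between (12 − 1) × 7 = 77 and (12 + 1) × 7 = 91 days. A year holds 365.25 / 84 = 4.3 intervals, so about 4 visits per year of follow-up. All of these are too late for the final observation and eligible for the maximum as written. Table 3 marks hematology at these visits but not chemistry.

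**3. When does a late value change a table?** Let m be the worst grade through last dose + 30 days and L the worst grade later. The tabulated maximum is the larger of m and L.
- The full shift table changes only if L > m.
- The Grade 0-2 to Grade 3-4 line changes only if baseline is Grade 0-2, m ≤ 2 and L ≥ 3.

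A hypothetical case: baseline Grade 1, m = 2, and a Grade 4 platelet count on day 84 after the last dose. The final-observation table ignores the count. The maximum-grade table records a shift to Grade 3-4.

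**4. Can the size be computed?** Take subjects with baseline Grade 0-2. Let a be the share who shift on treatment, r the share with off-treatment hematology, and p the chance of a later Grade 3-4 value among those without one on treatment. Treating these as independent, the added proportion is (1 − a) × r × p. None of the three is in the documents. Purely as assumptions:
- Low (a = 80%, r = 20%, p = 20%): 0.2 × 0.2 × 0.2 = 0.008, or 0.8 points.
- High (a = 40%, r = 50%, p = 60%): 0.6 × 0.5 × 0.6 = 0.18, or 18 points.

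If all 82 subjects at 600 mg were evaluable with baseline Grade 0-2, that is 0.7 to 14.8 subjects. The ratio of high to low is 0.18 / 0.008 = 22.5. The range shows only that the effect could be trivial or visible, so it is not an estimate.

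**The case against.** The strongest reply is that a 30-day limit is the natural reading. Adverse events, hospital days and the final observation all stop there, 7.7.1 presents the maximum-grade table as a counterpart of the final-observation table, and the protocol mentions unlimited time only for listings. Nor does the all-data sentence in 7.1 prove otherwise. The efficacy SAP uses similar wording in 8.1.8 and 8.1.9 while keeping last-dose + 30-day windows. That point stands: the sentence does not show that off-treatment values were meant to count. It does not supply the missing limit either, and a limit attached by name to the final observation does not carry over to the maximum.

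The exposure is also limited. Post-treatment visits apply only to subjects who stop for reasons other than progression, and they end at progression, death or refusal. Alternate anti-neoplastic therapy is a reason for discontinuation in protocol 5.4.1, so some subjects will have no counts under later treatment. Hematology is at least weekly in Cycles 1 and 2, so many subjects may already have reached their worst grade. All of this stands and narrows the consequence.

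A reader might infer that the SAP contradicts the protocol. It does not: 8.1.4.4 governs a different output, and 8.1.4.5 leaves the maximum without a window just as the SAP does. A reader might also infer that the maximum-grade shift is the main laboratory toxicity output. Nothing in the SAP ranks it so. A mismatch with the adverse event tables is not in itself a sign of error, because protocol 6.1.1.1 and 6.1.1.3 make laboratory abnormalities adverse events only under set conditions.

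**Conclusion.** The point holds as an omission shared by safety SAP 7.7.1 and 7.7.3 and protocol 8.1.4.5. Followed literally, the plan allows a scheduled off-treatment hematology value to become the tabulated worst grade when it exceeds the on-treatment maximum. The effect falls mainly on hematology parameters, and least on those where Grade 3-4 values are already near-universal on treatment.

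The size cannot be computed from the documents. It would be tempting to conclude that the tables will report toxicity from later therapy, transplant or relapse, or that rates will be materially inflated. The text supports only that such values can enter. The conclusion rests on two things: no end date appears anywhere for the maximum grade, and the post-treatment visits occur as scheduled.

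**What to change.** In safety SAP 7.7.1 and 7.7.3, define the maximum post-baseline grade as the highest grade among values collected after the first dose of study drug through last dose of study drug + 30 days. This matches the final-observation and adverse event windows. Keep later values in the Grade 3-4 listings, as protocol 8.1.4.5 provides.

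Do not also cut the window at the start of post-treatment therapy. Neither the final-observation rule nor the adverse event rule does so, and the shorter laboratory window would create a new mismatch.

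The cost is one sentence in the SAP and one date filter in the program. No new data are needed.

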7.7.2 Laboratory Abnormalities

Abnormal laboratory values will be summarized by following the search criteria in [Table 5](#).

Table 5. Laboratory Abnormalities

Laboratory Abnormalities	Search Criteria
Tumor Lysis Syndrome (Howard Criteria) (Howard SC et al. 2011)	≥ 2 of the following metabolic abnormalities within 24 hours of each other (applicable to post-dose laboratory values only): Uric Acid > 476 µmol/L or 8.0 mg/dL; Potassium > 6.0 mmol/L; Inorganic Phosphorus > 1.5 mmol/L or 4.5 mg/dl; corrected Calcium < 1.75 mmol/L or 7.0 mg/dl
Potential Drug-Induced Liver Injury	Post-dose laboratory ALT or AST > 3 × ULN in combination with total bilirubin > 2 × ULN that occur within 72 hours of each other

ALT = alanine aminotransferase; AST = aspartate aminotransferase; L = litre; µmol = micromole; mg/dL = milligram/deciliter; mmol = millimole; mEq = milliequivalent; ULN = upper limit of normal

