Appendix H. Tumor Lysis Syndrome Classification

Metabolic Abnormality	Criteria for Classification of Laboratory Tumor Lysis Syndrome*	Criteria for Classification of Clinical Tumor Lysis Syndrome**
Hyperuricemia	Uric acid > 8 mg/dl (475.8 µmol/liter)	N/A
Hyperphosphatemia	Phosphorus > 4.5 mg/dl (1.5 mmol/liter)	N/A
Hyperkalemia	Potassium > 6 mmol/liter	Cardiac dysrhythmia or sudden death probably or definitely caused by hyperkalemia
Hypocalcemia	Corrected calcium < 7.0 mg/dl (1.75 mmol/liter) or ionized calcium < 1.12 mg/dl (0.3 mmol/liter) [#]	Cardiac dysrhythmia, sudden death, seizure, neuromuscular irritability (tetany, paresthesias, muscle twitching, carpopedal spasm, Trousseau's sign, Chvostek's sign, laryngospasm, or bronchospasm), hypotension, or heart failure probably or definitely caused by hypocalcemia
Acute Kidney Injury [!]	N/A	Increase in the serum creatinine level of 0.3 mg/dl (26.5 µmol/liter) or the presence of oliguria (average urine output of < 0.5 ml/kg/hr over a 6-hour period)

* Laboratory TLS requires two or more metabolic abnormalities must be present during the same 24-hour period within 3 days before the start of therapy or up to 7 days afterward.

** Clinical TLS requires the presence of Laboratory TLS plus one or more findings from the Clinical TLS column.

Corrected calcium = measured calcium level in mg/dl + 0.8 × (4 – albumin in gm/dl).

! Acute kidney injury, unless attributable to another cause, represents clinical TLS even if criteria for laboratory TLS are not satisfied.

Cross reference: Howard SC 2011⁴³

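### Safety SAP Table 5 names the same published tumor lysis criteria as protocol Appendix H but omits the 7-day window, so later electrolyte pairs could be counted as laboratory TLS

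*SAP*

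**What the plan says.** Protocol Appendix H defines laboratory TLS as at least two metabolic abnormalities "during the same 24-hour period within 3 days before the start of therapy or up to 7 days afterward". Its calcium limb takes corrected calcium "or ionized calcium < 1.12 mg/dl (0.3 mmol/liter").

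Safety SAP Section 7.7.2, Table 5, has a TLS row that names the same 2011 source. It asks for at least two abnormalities "within 24 hours of each other (applicable to post-dose laboratory values only"). Its calcium limb is "corrected Calcium < 1.75 mmol/L or 7.0 mg/dl", with no ionized-calcium alternative. The row does not say that the published definition has been modified.

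Two general rules fix which data enter the search. SAP Section 7.1 states: "All data available in the extracted database will be used in the safety analyses". SAP Section 7.7 adds: "Data collected from the central and local laboratories, including additional laboratory testing due to an SAE, will be used in all analyses".

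**The concern.** The time window is part of the Appendix H definition: it ties a pair of abnormalities to the start of treatment. Without it, two abnormalities on one day several cycles later, for example high potassium with high phosphorus during sepsis or renal failure, would satisfy Table 5. SAE-triggered testing is included, so the late laboratory data come partly from subjects who are acutely ill.

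At stake is how the row can be read. A count carrying the name of published criteria will be compared with the protocol's own definition and with other studies that use it. As specified, it could mix ramp-up events with later organ dysfunction, and the table would not show which is which. Table 5 applies to analysis sets 2 and 3, so Study M14-358 is affected in the same way.

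**Working it through.** The plan gives no figure for this rule, so there is none to reproduce. The check compares the two texts, then counts the scheduled draws.

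**1. The definitions side by side**

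| Element | Protocol Appendix H | Safety SAP Table 5 |
|---|---|---|
| Uric acid | > 8 mg/dL (475.8 µmol/L) | > 8.0 mg/dL (476 µmol/L) |
| Potassium | > 6 mmol/L | > 6.0 mmol/L |
| Phosphorus | > 4.5 mg/dL (1.5 mmol/L) | > 4.5 mg/dL (1.5 mmol/L) |
| Corrected calcium | < 7.0 mg/dL (1.75 mmol/L) | < 7.0 mg/dL (1.75 mmol/L) |
| Ionized calcium | accepted | not mentioned |
| Pairing | same 24-hour period | within 24 hours |
| Before therapy | from 3 days before | excluded (post-dose only) |
| After therapy starts | up to 7 days | no limit |

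The four shared cut-offs agree apart from rounding. The missing upper limit can only add cases. The other two differences (no ionized calcium, no pre-therapy values) can only remove them.

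**2. Is the limit restored elsewhere?** The nearest time limits are both 30 days after last dose: one for the final observation (SAP 7.1), one for the longitudinal laboratory analysis (protocol 8.1.4.4). Neither is a 7-day limit on this search.

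**3. Scheduled chemistry draws outside the window**

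*Late draws.* Protocol Table 3 schedules chemistry on Day 1 of each cycle from Cycle 2, at the final visit and at the 30-day safety visit. For k cycles that is (k − 1) + 2:
- 6 cycles: 5 + 2 = 7
- 12 cycles: 11 + 2 = 13

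*Early draws, earlier schedule* (protocol 6.1.8.2, Protocol Version 1 and Amendment 1). There are four draws on each new-dose day, then draws 24, 48 and 72 hours after the first target dose. The 600 mg level has new doses on Days 2 to 6:
- (5 × 4) + 3 = 23, plus Day 1 from Table 3 = 24

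*Early draws, Cohort C* (protocol 6.1.8.2). There are two draws on each of Days 1 to 4 and one 24 hours after the maximal dose:
- (4 × 2) + 1 = 9

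*Share outside the window* = late / (late + early):

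| | 6 cycles | 12 cycles |
|---|---|---|
| Earlier schedule | 7/31 = 23% | 13/37 = 35% |
| Cohort C | 7/16 = 44% | 13/22 = 59% |

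**4. The anchor.** In Phase 1 and initial Phase 2, cytarabine starts on Day 1 and venetoclax on Day 2. At 600 mg the target dose is reached on Day 6, so the 72-hour draw falls on Day 9. Seven days from first venetoclax runs to Day 9 and includes it. Seven days from Day 1 runs to Day 8 and excludes it, which raises the shares to 8/31 = 26% and 14/37 = 38%. SAP 7.1 counts Study Day 1 from the first dose of study drug, defined there as venetoclax and LDAC, so without an instruction a programmer would probably anchor on Day 1.

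**5. What a late-pair rate would imply (assumption).** The documents give no frequency for late pairs. Let q be an assumed, independent chance of a qualifying pair at each late visit. The expected number of subjects with at least one, among the 82 at 600 mg, is 82 × [1 − (1 − q)^m], with m = 7 or 13:

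| q | 6 cycles (m = 7) | 12 cycles (m = 13) |
|---|---|---|
| 0.1% | 0.6 | 1.1 |
| 0.5% | 2.8 | 5.2 |
| 1% | 5.6 | 10.0 |

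Under Appendix H all of these are zero. The table treats every subject as completing the stated cycles and ignores unscheduled draws, so it is a scale and not an estimate.

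**The case against.** The strongest reply is that Table 5 is a descriptive laboratory search and contradicts no planned endpoint. Protocol Section 8.1.4 prescribes no laboratory TLS analysis, and Appendix H serves recognition, management and SAE reporting. That is correct, and it is why the point is minor. It does not explain why the row carries the name of criteria that it does not apply in full.

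Several stronger readings are tempting, and the documents do not support them:

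- **That TLS as an adverse event of special interest is distorted.** That summary points to SAP Section 7.6.2, where TLS is found by a narrow SMQ search of adverse events. Table 5 does not feed it.
- **That the case for simpler TLS management in Cohort C is undermined.** Protocol 6.1.8.2 rests that decision on the absence of clinical TLS. Table 5 has no clinical limb, and Amendment 2 (28 November 2016) predates safety SAP version 1.0 (13 December 2017).
- **That most chemistry data lie outside the window.** Counting visit days in Table 3 gives 7 of 12 (58%) for 6 cycles and 13 of 18 (72%) for 12. Footnote e of that table refers to Section 6.1.8.2, which requires several draws on each ramp-up day, so the shares above are the relevant ones. Even those measure opportunity, not a false-positive rate: a single late abnormality never counts.
- **That omitting ionized calcium loses cases.** It is in neither protocol Table 10 nor the TLS panels listed in Section 6.1.8.2, so the loss is largely hypothetical.

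A low or zero count under the wider rule would also still be reassuring for the period after dosing.

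A fair objection to the obvious remedy also stands. The protocol allows slower ramp-up and interruptions of up to 72 hours, so a genuine ramp-up event can fall after day 7. A bare date cut-off would discard it.

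**Conclusion.** The point holds and is minor. Table 5 names the source that Appendix H uses, shares its four main cut-offs and omits its upper time limit, and no other section supplies that limit. Qualifying pairs at any later time could therefore be counted as laboratory TLS under a name whose protocol definition excludes them.

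The size of the over-count is unknown. About 23% to 35% of scheduled draws (earlier schedule) or 44% to 59% (Cohort C) lie outside the window. This assumes 6 to 12 cycles, full adherence to the schedule, the 600 mg ramp-up, separate final and 30-day visits, and no unscheduled testing. The effect is confined to this laboratory row.

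**What to change.** In safety SAP Table 5:

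1. Report as laboratory TLS under the published criteria only post-dose pairs within the Appendix H window. State the anchor for start of therapy, for example the first venetoclax dose, because venetoclax starts on Day 2 in Phase 1 and initial Phase 2.
2. Tabulate all later post-dose pairs separately, with onset day and whether ramp-up was still in progress, so that no event is dropped.
3. Accept ionized calcium where it happens to be recorded (minor).
4. If the wider rule is kept, label the row as modified criteria and still split it by window.

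The cost is a line or two of SAP text, a date comparison, and a ramp-up flag derived from the dosing records. No new data are needed.

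This concerns only how laboratory results are classified and reported. It proposes no change to TLS monitoring or management.
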